7.2.3. Follow-Up

Subjects who enroll in Part 1 but not Part 2 will return to the study site for an End of Part 1 Evaluation approximately 4 months after the last dose of study treatment (End of Part 1 on Day 422 [± 7 days]).

In the event of a decision by the Sponsor to terminate the study earlier than the end of Part 1 based on emergent data from the Nusinersen clinical development program, subjects who do not elect to participate in Part 2 will complete their next evaluation after Part 1 is terminated and that visit will be the End of Part 1 Evaluation.

Subjects who enroll in Part 2 will have a Part 2 Final Follow-up Evaluation approximately 4 months after the last open-label dose of Nusinersen.

Subjects who withdraw early from Part 1 will be encouraged to complete the End of Part 1 Evaluation assessments at the time of withdrawal. Subjects who withdraw early from Part 2 will be encouraged to complete the Part 2 Early Termination Evaluation assessments at the time of withdrawal.

7.3. Study Stopping Rules

For Part 1 and Part 2 of the study, the Sponsor may terminate the study at any time by informing Investigators (who will subsequently inform the corresponding ethics committees) and any other applicable regulatory agencies. Investigators will be notified by the Sponsor if the study is placed on hold, completed, or closed.

Conditions that may warrant termination of the study include, but are not limited to, the following:

- The discovery of an unexpected, serious, or unacceptable risk to the subjects enrolled in the study.
- A decision on the part of the Sponsor to suspend or discontinue testing, evaluation, or development of the product.

7.4. End of Study

The end of the study is the last subject's completion of the last evaluation for Part 2.

7.5. Safety Monitoring and Data and Safety Monitoring Board

Safety data will be reviewed on an ongoing basis by the Sponsor and the Medical Monitor. Safety data will also be reviewed on a quarterly basis, throughout Part 1 of the study, by an independent Data and Safety Monitoring Board (DSMB; see Section [19.2](#)).

CONFIDENTIAL

The information contained herein may not be used, disclosed, or published without the written consent of Biogen MA Inc.

8. SELECTION OF SUBJECTS

8.1. Inclusion Criteria

To be eligible to participate in this study, candidates must meet the following eligibility criteria at Screening or at the time point specified in the individual eligibility criterion listed:

1. Ability of parent(s) or legal guardian(s) to understand the purpose and risks of the study and provide signed and dated informed consent and authorization to use confidential health information in accordance with national and local subject privacy regulations.
2. Genetic documentation of 5q *SMA* homozygous gene deletion, mutation, or compound heterozygote.
3. Onset of clinical signs and symptoms consistent with SMA at ≤ 6 months of age and have documentation of 3 *SMN2* copies.

OR

Onset of clinical signs and symptoms consistent with SMA at ≤ 6 months of age, > 7 months of age (211 days) at screening, and have documentation of 2 *SMN2* copies.

OR

Onset of clinical signs and symptoms consistent with SMA at > 6 months of age, are ≤ 18 months of age at screening, and have documentation of 2 or 3 *SMN2* copies.

4. Meets age-appropriate institutional criteria for use of anesthesia/sedation, if use is planned for study procedures (as assessed by the Investigator and either the anesthesiologist or pulmonologist).
5. Medical care, such as routine immunizations (including influenza vaccine, pneumococcus vaccine, and respiratory syncytial virus prophylaxis [palivizumab] if available), meets and is expected to continue to meet guidelines set out in the Consensus Statement for Standard of Care in SMA, in the opinion of the Investigator.
6. Subjects with 2 *SMN2* copies must reside within approximately 9 hours' ground-travel distance from a participating study site for the duration of the study. Residents who are > 2 hours' ground-travel distance from a study site must obtain clearance from the Investigator and the study Medical Monitor.
7. Able to complete all study procedures, measurements, and visits, and parent or legal guardian/subject has adequately supportive psychosocial circumstances, in the opinion of the Investigator.

For Part 2 only:

To be eligible to participate in Part 2 of this study, candidates must meet the following eligibility criteria at the time of consent to participate in Part 2:

1. Participation in Part 1 and completion of the End of Part 1 Evaluation assessments.
2. Ability of parent(s) or legal guardian(s) to understand the purpose and risks of the study and to provide signed and dated informed consent on the Part 2 informed consent form

CONFIDENTIAL

The information contained herein may not be used, disclosed, or published without the written consent of Biogen MA Inc.

(ICF) and authorization to use confidential health information in accordance with national and local subject privacy regulations.

3. Able to complete all study procedures, measurements, and visits, and parent or legal guardian/subject has adequately supportive psychosocial circumstances, in the opinion of the Investigator.

8.2. Exclusion Criteria

Candidates will be excluded from study entry if any of the following exclusion criteria exist at Screening or at the time point specified in the individual criterion listed:

1. Any previous exposure to Nusinersen; previous dosing in this study or previous studies with Nusinersen.
2. Signs or symptoms of SMA present at birth or within the first week after birth.
3. Ventilation for ≥ 16 hours per day continuously for >21 days at screening.
4. Permanent tracheostomy, implanted shunt for CSF drainage, or implanted CNS catheter at screening.
5. History of brain or spinal cord disease that would interfere with the LP procedure, CSF circulation, or safety assessments.
6. Hospitalization for surgery (e.g., scoliosis surgery), pulmonary event, or nutritional support within 2 months prior to screening, or hospitalization for surgery planned during the study.
7. Clinically significant abnormalities in hematology or clinical chemistry parameters or ECG, as assessed by the Investigator, at the Screening Visit that would render the subject unsuitable for inclusion.
8. Treatment with an investigational drug for SMA (e.g., albuterol/salbutamol, riluzole, carnitine, sodium phenylbutyrate, valproate, hydroxyurea), biological agent, or device within 30 days prior to screening. Any history of gene therapy, prior ASO treatment, or cell transplantation.
9. Ongoing medical condition that according to the Investigator would interfere with the conduct and assessments of the study. Examples are medical disability (e.g., wasting or cachexia, severe anemia) that would interfere with the assessment of safety or would compromise the ability of the subject to undergo study procedures.
10. The subject's parent or legal guardian is unable to understand the nature, scope, and possible consequences of the study, or does not agree to comply with the protocol's schedule of assessments.
11. Subject's parent or legal guardian is not willing to continue to meet standard of care guidelines for care (including vaccinations and respiratory syncytial virus prophylaxis if available), nor provide nutritional and respiratory support throughout the study.
12. Other unspecified reasons that, in the opinion of the Investigator or the Sponsor, make the subject unsuitable for enrollment.

CONFIDENTIAL

The information contained herein may not be used, disclosed, or published without the written consent of Biogen MA Inc.

For Part 2 only:

Candidates will be excluded from the Part 2 if they meet the following exclusion criterion at the time of consent into Part 2 of the study:

1. Any significant change in clinical status, including laboratory tests that, in the opinion of the Investigator, would make them unsuitable to participate in Part 2. The Investigator must reassess the subject's medical fitness for participation and consider any diseases that would preclude treatment.

Note that subjects who have been previously exposed to Nusinersen in Part 1 of the study (Exclusion criterion 1 for Part 1) may participate in Part 2.

9. ENROLLMENT, REGISTRATION, AND RANDOMIZATION

9.1. Screening and Enrollment

The subject's legally authorized representative (e.g., parent or legal guardian) must provide informed consent for Part 1 before study-specific screening tests are performed and for Part 2 before study-specific procedures are performed (see Section 17.3). When a subject's parent/guardian signs the ICF, that subject is assigned a unique subject identification number through the interactive response technology (IRT) system and is considered to be enrolled in the study. Participating study sites are required to document all screened candidates initially considered for inclusion in this study. If a subject is excluded from the study, the reasons for exclusion will be documented in the subject's source documents, within the IRT system, and on the screening log. If a subject initially fails any of the screening criteria, they will be allowed to be rescreened 1 time during the Screening Period, at the discretion of the Investigator.

9.2. Registration and Randomization of Subjects

In Part 1 of the study, subjects will be registered and randomized after all screening assessments have been completed and after the Investigator has verified that the subjects are eligible per criteria in Section 8.1 and Section 8.2. No subject may begin treatment until the subject is documented as registered (assigned a unique identification number) and is randomized for the study in the IRT system. Any subject identification numbers that are assigned will not be reused even if the subject does not receive treatment.

In Part 1 of the study, using an IRT system, eligible subjects will be randomized to receive Nusinersen:sham procedure in a 2:1 ratio. Randomization will be stratified based on age at onset of clinical signs and symptoms consistent with SMA: >6 months versus ≤6 months. Subjects who withdraw from the study may be replaced.

At the beginning of Part 2 of the study, the subject's treatment assignment will be unblinded via the IRT system. Part 2 is the OLE phase of the study in which all subjects receive Nusinersen.

Refer to the Study Reference Guide for details on registration and randomization.

CONFIDENTIAL

The information contained herein may not be used, disclosed, or published without the written consent of Biogen MA Inc.

9.3. Blinding Procedures

Part 1 of the study is a randomized, double-blind, sham-procedure controlled study. The Sponsor, parents and/or legal guardians, and key study site personnel will be blinded throughout Part 1 of the study. To maintain the study blind, it is imperative that subject treatment assignments are not shared with the subjects, their families, or any member of the study team, either at the study site or that of the Sponsor, except the unblinded site study staff (dedicated team) and the unblinded medical monitor or clinical research associate. The DSMB may be unblinded as described in the DSMB charter.

Before Part 2 Day 1, parents and/or legal guardians, key study site personnel, and the Sponsor will be unblinded to the treatment group to which the subjects were randomized in Part 1. This will be performed according to the unblinding plan, which will be finalized prior to unblinding. Of note, in the event that the Sponsor decides to rollover subjects to Part 2 early, unblinding for key study site personnel will occur prior to the End of Part 1 Evaluation in order to facilitate bringing subjects who were randomized to receive sham in Part 1 as soon as possible and to maintain the 4-month dosing interval for subjects who were randomized to receive Nusinersen in Part 2. Treatment in Part 2 will be open-label, and all study subjects will receive Nusinersen.

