The information contained herein may not be used, disclosed, or published without the written consent of Biogen MA Inc.

Statistical Methods: Analysis Population

The intent-to-treat population is defined as all subjects who are randomized and receive at least 1 dose of study treatment or sham procedure in Part 1.

The safety population will include all subjects who are randomized and receive at least 1 dose of study treatment or sham procedure in Part 1.

The PK population will include all subjects who are randomized and have at least 1 evaluable postdose or postsham-procedure PK sample.

Part 1**Safety Analysis**

The analysis of safety will be performed on the safety population. The incidence of treatment-emergent AEs and SAEs will be tabulated. Changes from baseline in clinical laboratory parameters, vital signs, and ECG parameters will be summarized. Incidence of clinically relevant changes from baseline in vital signs and ECGs will be summarized. Laboratory parameters will also be summarized using shift tables, as appropriate.

PK Analysis

Summary statistics for plasma and CSF concentrations of Nusinersen will be provided.

Exploratory Analysis

For continuous endpoints, the mean change from baseline will be estimated with 95% confidence limits. For categorical outcomes, the proportion of subjects attaining a specified category will be estimated. Selected endpoints may be pooled across subsets as appropriate.

Part 2

No formal statistical analyses will be performed. Descriptive statistics will be presented for safety and efficacy data collected.

Interim Analysis: No formal interim analyses are planned. However, if the Sponsor decides to terminate Part 1 early, data prior to the unblinding of the first subject in Part 1 may be archived; no analyses are planned to be conducted based on the archived data. Full analysis of Part 1 data will be done following database lock at the end of Part 1.

Sample Size Determination: Since this study is exploratory, sample size determination will not be based on power consideration. The sample size considered for this study will allow exploration of safety, tolerability, and selected efficacy endpoints in the selected study population.

CONFIDENTIAL

The information contained herein may not be used, disclosed, or published without the written consent of Biogen MA Inc.

Study Stopping
Rules:

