4.2. Schedule of Events

4.2.1. Schedule of Events: Part 1

Table 2: Part 1 Schedule of Activities

Study Period	Screen ¹	Part 1 Treatment/Follow-Up																	
		Days -28 to -1	Day 1			Day 2 ²	Day 15 (±1 day)			Day 16 ²	Day 29 (±1 day)			Day 30 ²	Days 64, 183, 302 (±7 days)			Days 65, 184, 303 ²	End of Part 1 ^{3,4,5}
			Predose	LP	Postdose		Predose	LP	Postdose		Predose	LP	Postdose		Predose	LP	Postdose		
Informed Consent	X																		
Inclusion/Exclusion Criteria	X	X																	
Medical History	X																		
Vital Signs ⁶	X	X		4X ⁷	X ⁸	X		X		X		4X ⁷		X		4X ⁷		X	
Weight	X	X			X	X				X				X				X	
Growth Parameters ⁹	X	X				X				X				X				X	
Physical Examination	X	X				X				X				X				X	
Ventilator Use	X	X			X	X			X	X			X	X			X	X	
Neurological Examination ¹⁰	X	X		X ¹¹	X	X		X ¹¹		X		X ¹¹		X		X ¹¹		X	
ECG	X				X							X						X	
Safety Laboratory Tests ¹²	X													X ¹³				X ¹⁴	
Coagulation Laboratory Tests	X																		
Immunogenicity Sample		X												X				X	
CSF PK ¹⁵		X				X				X				X					
Plasma PK				X ¹⁶										X ¹⁷				X	
Study Treatment Injection or Sham			X				X				X				X				

CONFIDENTIAL

The information contained herein may not be used, disclosed, or published without the written consent of Biogen MA Inc.

Study Period	Screen ¹	Part 1 Treatment/Follow-Up																
Study Day	Days -28 to -1	Day 1			Day 2 ²	Day 15 (±1 day)			Day 16 ²	Day 29 (±1 day)			Day 30 ²	Days 64, 183, 302 (±7 days)			Days 65, 184, 303 ²	End of Part 1 ^{3,4,5}
		Predose	LP	Postdose		Predose	LP	Postdose		Predose	LP	Postdose		Predose	LP	Postdose		
Procedure																		
Inpatient Stay ¹⁸				X														
Telephone Contact for Safety Monitoring ²								X					X				X	
HINE Motor Milestone		X												X				X
Clinical Global Impression of Change														X				X
Con Med Recording ¹⁹		X ----- X																
Adverse Event Collection ²⁰		X ----- X																

AE = adverse event; Bi-PAP = bilevel positive airway pressure; Con Med = concomitant medication; CSF = cerebrospinal fluid; ECG = electrocardiogram; HINE = Hammersmith Infant Neurological Examination; LP = lumbar puncture; PK = pharmacokinetic(s); SAE = serious adverse event; SMA = spinal muscular atrophy; *SMN2* = survival motor neuron 2

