6.3. Exploratory Objectives and Endpoints

Part 1

The exploratory objective of Part 1 of this study is:

- To explore the efficacy of Nusinersen in subjects with SMA who are not eligible to participate in the clinical studies ISIS 396443-CS3B or ISIS 396443-CS4.

The endpoints that relate to this objective are:

- Change from baseline in ventilator use
- Attainment of motor milestones assessed by Section 2 of the Hammersmith Infant Neurological Examination (HINE)
- Change from baseline in growth parameters (body length, head circumference, chest circumference, arm circumference, weight for age, weight for length, and head to chest circumference ratio) through final safety follow-up evaluation
- Clinical Global Impression of Change (physician and caregiver assessment) through final safety follow-up evaluation

The exploratory immunogenicity endpoint is as follows:

- Plasma antibodies to Nusinersen

Part 2

The exploratory objective of Part 2 of this study is:

- To explore the efficacy of Nusinersen in subjects with SMA who participated in Part 1 and completed their End of Part 1 Evaluation assessments.

The endpoints that relate to this objective are:

- Change from baseline in ventilator use
- Attainment of motor milestones assessed by World Health Organization (WHO) motor milestones and Section 2 of the HINE
- Change from baseline in growth parameters (body length, head circumference, chest circumference, arm circumference, weight for age, weight for length, and head to chest circumference ratio) through Part 2 Final Follow-up Evaluation
- Clinical Global Impression of Change (physician and caregiver assessment) through Part 2 Final Follow-up Evaluation and Assessment of Caregiver Experience with Neuromuscular Disease (ACEND)

CONFIDENTIAL

The information contained herein may not be used, disclosed, or published without the written consent of Biogen MA Inc.

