9.3.1. Emergency Unblinding of Treatment Assignment

In Part 1 of the study, if a subject has experienced an SAE (as defined in Section 15.1.2), and/or when knowledge of the treatment assignment will impact the clinical management of the subject, the Investigator will have the ability to unblind the treatment assignment for that subject using the IRT. However, prior to unblinding, the Investigator should attempt to contact the blinded Medical Monitor to discuss the emergency. The Sponsor or designee will be informed of the unblinding of a subject within 24 hours. Every reasonable attempt should be made to complete the End of Part 1 Evaluation assessments prior to unblinding, as knowledge of the treatment arm could influence subject assessment. The Investigator must document the reasons for unblinding in the subject's source documents. The Investigator is strongly advised not to divulge the subject's treatment assignment to any individual not directly involved in managing the medical emergency, nor to personnel involved with the analysis and conduct of the study. In cases where there are ethical reasons to have a subject whose treatment assignment was unblinded for safety reasons remain in the study, the Investigator must obtain specific approval from the Sponsor and the Medical Monitor for the subject to continue in the study.

In addition, all suspected unexpected serious adverse reactions (SUSARs) will be unblinded by the Sponsor's (or designee) Drug Safety and Quality Assurance personnel for the purpose of regulatory reporting (Section 15.3.4).

CONFIDENTIAL

The information contained herein may not be used, disclosed, or published without the written consent of Biogen MA Inc.

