11.1.1. Study Treatment

In Part 1 of the study, each subject will receive a single intrathecal bolus (1 to 3 minutes) LP injection of Nusinersen or sham procedure on Days 1, 15, 29, 64, 183, and 302 by dedicated study personnel who are unblinded to treatment group; this cannot be any of the key study site personnel (i.e., the Investigator, the study coordinator, or outcome assessors). The study treatment administration will be performed in a dedicated room, and key study personnel and the parents will not be present during the procedure to ensure blinding.

In Part 2 of the study, each subject will receive a single intrathecal bolus (1 to 3 minutes) LP injection of Nusinersen at the days determined by their Part 1 treatment assignment as specified in Table 3 and Table 4. Treatment administration will not be blinded.

Nusinersen will be administered using a "spinal anesthesia" needle and a 5-mL syringe. A 22G to 25G spinal anesthesia needle is recommended based on subject size or clinical condition. The target site for needle insertion is the L3/L4 space but may be 1 segment above or 1 to 2 segments below this level, if needed. Depending on institutional guidelines, anesthesia may be used for the LP procedure or for the sham procedure in Part 1, following institutional procedures. Spinal ultrasound or other imaging techniques may be used to guide the intrathecal administration of Nusinersen if deemed necessary, but these are not required. Subjects will be encouraged to lie down flat for 1 hour following injection of the study treatment, if possible. Prior to each injection, 0.5 mL of CSF fluid will be collected for analyses. CSF will be used for Nusinersen PK analyses. Upon consent, extra CSF and blood samples will be stored for optional future investigation of possible biomarkers of SMA disease (e.g., CSF mRNA, CSF protein, CSF microRNA panel) or for profiling of drug binding proteins, bioanalytical method validation purposes, stability assessments, metabolite assessments, immunogenicity assessments (including assay development and validation purposes), or other actions of Nusinersen with CSF constituents. CSF analyses and data presentation will be conducted in a blinded manner in Part 1.

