#### Missing data

##### *Part 2 analysis*

For Part 2 HINE motor milestones, Baseline will be retrieved from Part 1 and it will be the last assessment in Part 1.

Some general rules for the approaches to imputation of missing data are described in the following sections.

- 1) If a subject has any milestones missing at baseline then the missing milestone will be imputed using the median baseline value within the age of SMA onset ( $\leq 6$  months,  $>6$  months). for the correspondent milestone level
- 2) If a subject has any missing milestones at any visit that is not last visit, then the missing milestone will be imputed using a linear interpolation at the milestone level for any actual scheduled study visits.
- 3) If a subject has any missing milestones at last visit, then the missing milestone will be imputed using the lowest observed value for milestone assigned within the age of SMA onset ( $\leq 6$  months,  $>6$  months) and group to which the subject belongs at that visit (e.g., if a previous control subject's last visit is Day 120, then the at lowest observed value for the previous control group at Day 120 is used for the non-missing values for the specific motor milestone).

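### On early roll-over, site raters may know the arm at the End of Part 1 HINE, physician CGIC and neurological examination, and the integrated SAP reuses those ratings with no flag or sensitivity analysis

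*Protocol*

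**What the plan says.** Protocol 9.3 keeps the sponsor, families and key site staff blinded during Part 1, then makes an exception for early roll-over: "unblinding for key study site personnel will occur prior to the End of Part 1 Evaluation". The reasons given are to bring sham children in quickly and to hold the dosing interval for children on nusinersen. Section 11.1.1 shows who these staff are when it says of the unblinded person giving the procedure: "this cannot be any of the key study site personnel (i.e., the Investigator, the study coordinator, or outcome assessors".

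For emergency unblinding, Section 9.3.1 asks sites to finish the End of Part 1 assessments first, "as knowledge of the treatment arm could influence subject assessment".

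In Protocol Table 2, the "HINE Motor Milestone" row is marked at Day 1 predose, Days 64, 183 and 302, and End of Part 1. CGIC is marked on the same post-baseline days, and the neurological examination is also done at End of Part 1. Section 6.3 lists the "Clinical Global Impression of Change (physician and caregiver assessment) through final safety follow-up evaluation" as a Part 1 endpoint, so there are two raters.

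On the data, the Synopsis says that what was collected before the first subject is unblinded may be archived, that "no analyses are planned to be conducted based on the archived data", and that "Full analysis of Part 1 data will be done following database lock at the end of Part 1".

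The SAP (Sections 1, 1.3 and 2) confirms that Part 1 stopped early and that sham children left first, whatever their planned dosing days. Its Section 2 defines an efficacy column for previous controls in Part 1. Section 4.5.1 repeats the HINE responder analysis at the last available assessment and says, for the Part 2 analysis: "Baseline will be retrieved from Part 1 and it will be the last assessment in Part 1".

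**The concern.** HINE, the physician CGIC and the neurological examination all depend on judgement. The protocol itself accepts that knowing the arm can influence them, yet for early roll-over it reverses the order that it asks for in an emergency. The early roll-over rule then came into use.

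The End of Part 1 visit closes the only randomised, sham-controlled period. In the supplied SAP, ratings from that visit sit beside blinded ones under the same visit label. For HINE, the rating is also the starting point for Part 2 change. HINE and CGIC are exploratory, but change in neurological examination is a primary endpoint (Protocol 6.1 and the note in 16.2.2.1). SAP 5.5 also restricts the integrated display to changes judged not secondary to SMA, and that judgement could be swayed by knowledge of the arm.

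**Working it through.** The documents give no figure for assessor bias, power or effect size, so there is no plan figure to reproduce. The check compares sections and adds simple arithmetic.

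**1. Order of unblinding and rating.**

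| Source | When unblinding occurs |
|---|---|
| Protocol 9.3, general rule | Blinded through Part 1; unblinded before Part 2 Day 1 |
| Protocol 9.3, early roll-over | Site staff unblinded before the End of Part 1 Evaluation |
| Protocol 9.2 | At the beginning of Part 2 |
| Table 2, footnote 5 | At the End of Part 1 evaluation |
| Protocol 9.3.1, emergency | After the End of Part 1 assessments, where possible |

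These timings differ. Only the early roll-over sentence places unblinding before the ratings.

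**2. Share of HINE ratings affected.** Under Protocol 7.2.2, the next evaluation after early termination becomes End of Part 1. A child with k completed visits among Days 64, 183 and 302 has k + 1 post-baseline HINE ratings, one of them at End of Part 1. The share is 1/(k + 1):

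- k = 0 (stopped before Day 64): 1 of 1
- k = 1: 1 of 2
- k = 2: 1 of 3
- k = 3: 1 of 4

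The documents do not say how many children fall in each row.

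**3. Where the SAP carries the rating.**
- Windowing (SAP 4.1): an End of Part 1 rating on study day 150, for example, lies in the window above 123 and up to 242, so it is labelled Day 183 like a blinded Day 183 rating.
- Last available assessment (SAP 4.5.1): in the sham Part 1 column, this is the End of Part 1 rating whenever HINE was done there.
- Part 2 baseline (SAP 4.5.1): HINE only. Protocol Tables 3 and 4 schedule no HINE on Part 2 Day 1, so nothing replaces it.
- CGIC (SAP 4.6): each score is relative to admission to Part 1 or Part 2, so no End of Part 1 CGIC serves as a baseline.

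**4. Direction.** Suppose that a sham child's End of Part 1 HINE is scored d points too low. Part 1 change is End of Part 1 minus Part 1 baseline, so it falls by d and the nusinersen-minus-sham difference grows. Part 2 change is the later value minus End of Part 1, so it rises by d. Both movements favour nusinersen. As an assumption only, a mean shift of 0.5, 1 or 2 points in the sham arm alone moves the mean difference by 0.5, 1 or 2 points. The same shift in opposite directions in the two arms moves it by 1, 2 or 4.

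**5. Weight of one child.** Planned sizes are 14 nusinersen and 7 sham (Protocol 7.1).
- One sham responder changed: 1/7 = 14.3 points.
- One nusinersen responder changed: 1/14 = 7.1 points.
- One in each arm, in opposite directions: 1/7 + 1/14 = 21.4 points.

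**6. Age of the last blinded HINE.** The gaps between scheduled ratings are 183 − 64 = 119 days, 302 − 183 = 119 days and 422 − 302 = 120 days, so it can be about 4 months older. For a child stopped before Day 64 it is the Day 1 value.

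**The case against.** The early unblinding was deliberate, disclosed and given a reason. HINE and CGIC are exploratory and the trial is unpowered. All earlier blinded visits still enter the Part 1 analysis. Unblinding follows a separate plan and Part 1 has its own SAP; neither was supplied, and either could provide a blinded rater or an analysis cut at unblinding. The explicit HINE baseline rule serves the Part 2 analysis, which is a limited set of summaries. For children first given nusinersen, the integrated analysis treats both parts as one period, so End of Part 1 is only an intermediate visit there. Off-schedule sham visits could also have revealed the arm to raters who had not been told.

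These points limit the concern but do not remove it, because the supplied SAP reuses the ratings without marking them. They do rule out several stronger readings that a reader might infer:

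- *That caregivers rated unblinded.* The early roll-over sentence covers site staff. Families are unblinded before Part 2 Day 1, and the order relative to the caregiver CGIC is not stated.
- *That CGIC also becomes a Part 2 baseline.* SAP 4.6 shows that it does not.
- *That bias in Part 1 reverses in Part 2.* For sham children a low rating favours nusinersen in both parts.
- *That an archive of blinded data is ready to use.* Archiving is optional, and its cut is study-wide at the first unblinding, so it would drop blinded visits made later.
- *That no safeguard exists.* The two missing documents prevent that conclusion.

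**Conclusion.** The concern holds in limited form. For children rolled over early, the End of Part 1 HINE, physician CGIC and neurological examination may have been rated with the arm known, contrary to the order that the protocol prefers in its own emergency rule. For HINE this is 1 of 1 to 1 of 4 post-baseline ratings per child. The supplied SAP gives a reader no means of seeing whether its results depend on them.

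The conclusion assumes that sites followed Section 9.3 as written and that the unseen documents add no blinded rater. The responder-rate movements of 14.3 and 7.1 points use planned arm sizes and show how much one child weighs; they are not estimates of bias. The documents do not support saying that the randomised comparison is invalid or that bias occurred.

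**What to change.** In the integrated SAP:

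1. Record each child's unblinding date and flag every Part 1 rating made after it, in both arms. Do not rely on the optional archive.
2. Add a named sensitivity analysis that repeats, without flagged ratings, the HINE and physician CGIC displays for previous controls in Part 1 (including the responder analysis at last available assessment) and the neurological examination shifts.
3. In the same analysis, repeat the Part 2 HINE change using the last blinded HINE as baseline.
4. State whether caregivers had been unblinded before their End of Part 1 CGIC, and reconcile the unblinding timings in Protocol 9.2, 9.3 and Table 2 footnote 5.

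The cost is some SAP wording and a few repeated tables, with no new assessments of the children. The downside is that the last blinded HINE is older, so some untreated change in sham children would enter their Part 2 change, and a blinded baseline would be set against open-label ratings. A child stopped before Day 64 would contribute no post-baseline blinded HINE. For these reasons it should stand beside the main analysis and not replace it. Changing the order of unblinding in Section 9.3 would have little effect now that Part 1 has ended.
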